5.10 Determination of Sample Size

This study is designed to provide a sufficient number of events to build and evaluate a prediction model. The planned sample size of 800 subjects will continue until at least 80 ischemic events have occurred. Under the guideline from Steyerberg of 10 events required per predictor (Steyerberg 2019), this sample size will allow a model with FcγRIIa and up to seven additional predictors to be built. Preliminary results ([name] 2018) suggest that a 4-fold greater incidence of events will be seen in subjects with high platelet expression of FcγRIIa. For the primary endpoint, there will be at least 95% power to detect a 2-fold greater incidence of cardiovascular endpoints (MI, stroke, and death) with a two-sided $\alpha < 0.01$ assuming 8% of subjects experience the endpoint. With the planned sample size of 800 a hazard ratio (HR) of 1.9 with a $p=0.04$ (lower bound of the 95% CI of 1.2) can be detected. For the secondary endpoint, there will be 95% power to detect a hazard ratio of 1.93 when comparing bleeding risk in subjects with high compared with low FcγRIIa expression when assuming a two-sided $\alpha = 0.05$ and 5% of subjects experience bleeding in the low FcγRIIa expression group.

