#### 9.2 SAMPLE SIZE DETERMINATION

This study is designed to provide a sufficient number of events to build and evaluate a prediction model. The planned sample size of 800 subjects will continue until at least 80 ischemic events have occurred. Under the guideline from Steyerberg of 10 events required per predictor (Steyerberg 2019), this sample size will allow a model with FcγRIIa and up to seven additional predictors to be built. Preliminary results ([name] 2018) suggest that a 4-fold greater incidence of events will be seen in subjects with high platelet expression of FcγRIIa. For

the primary endpoint, there will be at least 95% power to detect a 2-fold greater incidence of cardiovascular endpoints (MI, stroke, and death) with a two-sided  $\alpha < 0.01$  assuming 8% of subjects experience the endpoint. With the planned sample size of 800 a hazard ratio (HR) of 1.9 with a  $p=0.04$  (lower bound of the 95% CI of 1.2) can be detected. For the secondary endpoint, there will be 95% power to detect a hazard ratio of 1.93 when comparing bleeding risk in subjects with high compared with low FcγRIIa expression when assuming a two-sided  $\alpha=0.05$  and 5% of subjects experience bleeding in the low FcγRIIa expression group.

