#### 9.4.2 ANALYSIS OF THE PRIMARY OBJECTIVE

Cox proportional hazards models will be fit to compare the risk of the primary endpoint based on platelet expression of FcγRIIa as a continuous variable. Subjects will be followed until their earliest MI, stroke, or death. Patients who do not experience the composite endpoint will be censored at their last telephone follow-up. Time to the primary endpoint will be calculated as days from study enrollment. Models will be adjusted for potential confounders including sex and other subject demographics and medical history collected at baseline. In the pilot study, it was observed that older age, diabetes mellitus, and prior revascularization were associated with higher platelet FcγRIIa expression.

A set of sensitivity analyses will evaluate FcγRIIa as a binary endpoint, which each analysis using a different threshold for classifying FcγRIIa as high or low. In particular, these analyses will explore whether a binary or a continuous measure of FcγRIIa provides greater predictive value, and whether or not a threshold of  $\geq 11,000/\text{platelet}$  is optimal.

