5.7 Statistical Methods

5.7.1 Analysis of the Primary Objective

The primary analysis of the primary endpoint will be a Cox proportional hazards model. The dependent variable is the number of days from enrolment to the occurrence of a primary endpoint, with censoring at the last day of complete follow-up; independent variables will be FcγRIIa (measured in thousands), age in years, history of diabetes mellitus, prior revascularization, multi-vessel coronary artery disease (MVD) defined as ≥2 vessels or left main with a stenosis ≥50%, chronic kidney disease (CKD) defined as estimated glomerular filtration rate (GFR) < 60 ml/min/1.73 m², prior MI, hypertension, tobacco use, heart failure or LVEF<30%, previous stroke or transient ischemic attack, and peripheral arterial disease. Interest is in the FcγRIIa parameter: point estimate (increase in risk per 1000-unit increase in FcγRIIa), confidence interval and p-value. FcγRIIa will be declared to be associated with cardiovascular risk if the 2-sided p-value from this model is < 0.05.

A set of exploratory/sensitivity and subgroup analyses based on the Cox model will also be conducted.

- Instead of censoring at the last day of complete follow-up, censor at the last day of vital status follow-up
- FcγRIIa as the only covariate in the model
- Separate analyses of each component of the primary endpoint: MI and stroke, both censored at the last day of complete follow-up, and death, censored at the last day of vital status follow-up
- Run the primary model in subgroups defined by age (in decades), sex, history of diabetes and prior revascularization (including all covariates except the subgroup variable in the model)
- Run the primary model with the use of DAPT (any use prior to a primary endpoint), and its interaction with FcγRIIa, as additional covariates

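### The 95% power stated for the primary endpoint belongs to a high-versus-low comparison at alpha below 0.01, not to the continuous, adjusted Cox test that decides the study, and it does not follow from its own inputs

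*SAP*

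**What the plan says.** **Sizing (SAP 5.10, same text in Protocol 9.2).** The power sentence reads "For the primary endpoint, there will be at least 95% power to detect a 2-fold greater incidence of cardiovascular endpoints (MI, stroke, and death"). Its other inputs are a two-sided alpha below 0.01 and an event proportion of 8%. That sentence does not name its groups. The one before it does, because it says that pilot results "suggest that a 4-fold greater incidence of events will be seen in subjects with high platelet expression". The bleeding sentence later in the paragraph also compares high with low expression. The contrast is therefore between two groups.

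**Decision rule (SAP 5.7.1).** In the primary Cox model the "independent variables will be FcγRIIa (measured in thousands), age in years, history of diabetes mellitus", followed by nine more terms: FcγRIIa plus 11 other covariates in all. The parameter of interest is the effect per 1,000 units, and the rule is "FcγRIIa will be declared to be associated with cardiovascular risk if the 2-sided p-value from this model is < 0.05".

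**Protocol 9.4.2.** The primary comparison is "based on platelet expression of FcγRIIa as a continuous variable", and binary versions are sensitivity analyses. The same section notes that in the pilot "older age, diabetes mellitus, and prior revascularization were associated with higher platelet FcγRIIa expression".

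Neither document gives an SD for FcγRIIa, a hazard ratio per unit or per SD, an allowance for correlation with covariates, or a power for the continuous coefficient.

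**The concern.** The power sentence is presented as that of the primary endpoint, but three of its ingredients differ from the primary test. The effect is a ratio between two classes, not a slope. The alpha is below 0.01, not 0.05. Nothing is said about information lost to covariates, although the protocol reports that age, diabetes and prior revascularization go with higher FcγRIIa and the SAP puts all three in the model.

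What is at stake is interpretation. If the primary p-value exceeds 0.05, readers will set that result against a printed 95% that was not computed for that test. Correcting the two-group number alone would still leave the plan without a power statement for its primary analysis.

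**Working it through.** **1. The plan's own figure.** Inputs from SAP 5.10: 800 subjects; 8% with an event, so D = 0.08 × 800 = 64; ratio 2, treated as HR 2; two-sided alpha 0.01. The share of subjects in the high group is not given there, so 50% is assumed. Protocol 2.3 reports 55% in clinically high-risk pilot patients, which changes little.

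Schoenfeld: power = Φ(√(D·p(1−p))·ln HR − z₀.₉₉₅), with ln 2 = 0.693 and z₀.₉₉₅ = 2.576.

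- D = 64: √16 × 0.693 − 2.576 = 0.197, power 58% (two-proportion formula 58%; 57% with 55% high).
- D = 80, the minimum in the stopping rule: √20 × 0.693 − 2.576 = 0.524, power 70%.
- Events for 95%: (2.576 + 1.645)² / (0.25 × 0.693²) = 148.3, so 149.

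Reading 8% as the low-group rate (96 events) gives 79–82%. Across the variants tried at alpha 0.01, one- or two-sided, the highest power was 88%.

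**2. The primary test.** For a continuous Cox covariate:

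power = Φ(√(D(1−R²))·|ln HR per SD| − z₀.₉₇₅), with z₀.₉₇₅ = 1.960.

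R² is the share of FcγRIIa variance explained by the other covariates. To link this to a 2-fold contrast one must assume a distribution and a shape, and the documents supply neither.

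*Log-linear effect, normal FcγRIIa, median split.* The halves differ in mean by 2√(2/π) = 1.596 SD. An average 2-fold contrast is then ln 2 / 1.596 = 0.434 per SD, or HR 1.54 per SD. At alpha 0.05:

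| Events | R² = 0 | R² = 0.2 |
|---|---|---|
| 64 | 8.00 × 0.434 − 1.960 = 1.515; 94% | 7.16 × 0.434 − 1.960 = 1.148; 87% |
| 80 | 8.94 × 0.434 − 1.960 = 1.925; 97% | 8.00 × 0.434 − 1.960 = 1.515; 94% |

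Simulation with a log-normal FcγRIIa (log-SD 0.3 to 0.5) and a linear effect gives 98% to almost 100% unadjusted.

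*Pure step effect, HR 2 at the median and flat on either side.* For a normal variable the squared correlation between the value and its median split is 2/π = 0.637, so power ≈ Φ(√(D × 0.25 × 0.637) × 0.693 − 1.960). This is 60% with 64 events and 70% with 80. Simulated score tests (normal, then log-normal with log-SD 0.3 and 0.5) gave 59/54/48% with 64 events and 67/63/57% with 80.

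**3. Effects the primary test can detect.** HR per SD = exp((1.960 + z_power)/√(D(1−R²))), for 80 events at alpha 0.05:

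| R² | 80% power | 95% power |
|---|---|---|
| 0 | exp(2.802/8.944) = 1.37 | exp(3.605/8.944) = 1.50 |
| 0.2 | exp(2.802/8.000) = 1.42 | exp(3.605/8.000) = 1.57 |

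**The case against.** **A continuous analysis uses more information, so the two-group figure is conservative.** Protocol 2.3 expects the continuous measure to be more predictive than the dichotomous one. Under a log-linear effect, which is the form the primary model fits, the primary test has about 97% power at 80 events before adjustment. That stands, and it is why no shortfall is claimed. It is not a guarantee. If risk changes mainly at a threshold, which the plan also investigates, the slope test loses power. The sizing paragraph states no shape.

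**Alpha below 0.01 is stricter than 0.05.** For one and the same test this is true and harmless. Here the test differs too, so the stricter alpha does not make 95% a lower bound.

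**The study is sized on events per predictor, and more than 80 events are likely.** Both sections do open with the prediction model. Protocol 4.1 anticipates a 10% annual event rate, 12 months of enrolment and at least 18 months of follow-up. With hazard 0.10 and uniform entry that gives 800 × [1 − (e^−0.15 − e^−0.25)/0.10] ≈ 145 events, at which the two-group power is 94.5%. But 145 events is about 18% of subjects, not the 8% stated, and the result is still a two-group figure.

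**The sizing may have allowed for covariates.** The text is silent, so one can say only that no allowance is stated.

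**Conclusion.** The point holds as a mismatch between sizing and analysis, together with a figure that its stated inputs do not reproduce. The printed 95% is for a high-versus-low contrast at alpha below 0.01. The deciding test is the adjusted continuous coefficient at 0.05, for which the documents give no power. As a two-group figure the inputs yield about 58% (64 events) or 70% (80 events), assuming about half the subjects are high.

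A reader might infer that the primary test is underpowered. The documents do not support that. For an average 2-fold contrast, unadjusted power at 0.05 with 64 to 80 events lies between about 48–67% (step) and about 94–100% (log-linear). Correlation with covariates lowers these: in the normal log-linear case an assumed R² of 0.2 leaves about 87% and 94%. The low end needs a pure step with no gradient on either side, which the plan does not assert. The median split, the distribution, the shape and R² are all assumptions. The width of the range shows that the stated figure cannot be carried over to the primary test; it does not show a deficit.

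**What to change.** In SAP 5.10 and Protocol 9.2, replace the primary power sentence with the power of the SAP 5.7.1 test, for example:

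> With 80 first events and two-sided alpha 0.05, the adjusted Cox coefficient of continuous FcγRIIa has 80% power for HR 1.37 per SD and 95% power for HR 1.50 per SD if R² with the covariates is 0, or for HR 1.42 and 1.57 per SD at an assumed R² of 0.2.

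Then convert to the reporting unit with HR per 1,000 = (HR per SD)^(1,000/SD). The SD should come from the baseline FcγRIIa results, taken without reference to outcomes. Stating the effect per SD first also avoids tying it to pilot units, since SAP 5.7.1 explains that the assay scale changed (11,000 became about 1,750).

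If a high-versus-low figure is kept, recompute it from stated inputs (event count, share high, alpha) and label it as the power of the binary sensitivity or exploratory analysis, in line with Protocol 9.4.2 and SAP 5.7.1.

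The cost is wording in two sections. Enrolment, follow-up and the primary model do not change. The downside is that the printed power becomes less favourable and depends openly on a stated SD and R².

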The predictive capacity of platelet expression of Fc $\gamma$ RIIa was evaluated. The sensitivity of high expression to identify patients with cardiovascular events was 0.82 (95% CI 0.57 - 0.92) and the specificity was 0.51 (95% CI 0.43 - 0.58). MI, stroke, and death were uncommon (8% of all patients) in patients who had had an MI. The negative predictive value of low platelet expression of Fc $\gamma$ RIIa was 0.97 (95% CI 0.89 - 0.98) and the positive predictive value of high platelet expression of Fc $\gamma$ RIIa was 0.14 (95% CI 0.10 - 0.46). While identification of patients at high risk has great value, the identification of patients at low risk is important to reassure clinicians that they can safely withhold therapy that is associated with a risk of complications. As is often the case for low prevalence events, the negative predictive value of platelet Fc $\gamma$ RIIa expression (97% [95% CI 89% - 98%]) offers potentially important guidance to clinicians.

A key objective of this study is to determine the optimal threshold of platelet Fc $\gamma$ RIIa expression that classifies patients as high and low risk that will, in turn, be incorporated into an individualized score designed to predict patient risk. Assessment of platelet Fc $\gamma$ RIIa expression as a continuous variable is expected to be more predictive than as a dichotomous variable. If assessment of platelet Fc $\gamma$ RIIa expression as a dichotomous variable is nearly as predictive as a continuous variable, then the simplicity associated with the definition of a threshold for high and low risk could be preferred.

Clinical criteria that identify patients at increased risk of thrombosis also identify an increased risk of bleeding (Lindholm 2019). A key feature predisposing to both thrombosis and bleeding is older age. Not surprisingly, patients identified as having an increased risk of ischemic events also exhibit a higher risk of bleeding events (Hsieh 2017, Lindholm 2019). In this pilot study, increased platelet expression of Fc $\gamma$ RIIa was not associated with a greater risk of bleeding

([name] 2018). Further, a meta-analysis of platelet function tests demonstrated that patients with high platelet reactivity were at lower risk of bleeding events compared with those who exhibit low platelet reactivity (Aradi 2015).

In summary, preliminary results demonstrate:

- Increased platelet FcγRIIa expression is associated with consistently increased platelet reactivity

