The primary endpoint will be the composite of death, MI, and stroke. MI will be defined in accordance with the 4th universal definition (Thygesen 2018) and stroke consistent with consensus guidelines (Sacco 2013). The incidence of clinically significant bleeding will be determined using the Bleeding Academic Research Consortium (BARC) scale (Mehran 2011) and is defined as BARC type 2-5. Study endpoint events will be confirmed by the review of medical records by the investigator and all relevant medical records will be obtained by the site for submission to the sponsor (as described in Section 10.8). Subjects who experience an endpoint event will continue to be followed throughout the entire study and any subsequent endpoint events will also be confirmed and recorded. See Appendix 1 for study endpoint event definitions.

A total of approximately 800 subjects will be enrolled at approximately 10-20 sites in the US. It is anticipated that it will take about 12 months to enroll the total number of subjects. The study and subject follow-up will continue until 1) at least 80 ischemic events (MI, stroke, and death) have occurred, and 2) the last subject enrolled has completed at least 18 months of follow-up. Based on an annual ischemic event rate of 10%, the overall length of participation in the study is anticipated to be up to 3 years. Results will be monitored during the course of the study.

Figure 5 Schematic Overview of the Study

MI=myocardial infarction; NSTEMI= non-ST-segment elevation MI, STEMI= ST-segment elevation MI

\* Subjects who experience an endpoint event will continue to be followed throughout the entire study and any subsequent events will also be confirmed and recorded.

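### The stated 95% power for the primary endpoint is about 57% on its own inputs, and HR 1.9, p=0.04 and a lower limit of 1.2 cannot occur together

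*SAP*

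**What the plan says.** SAP 5.10 and Protocol 9.2 carry the same paragraph. For the primary endpoint it states that "there will be at least 95% power to detect a 2-fold greater incidence of cardiovascular endpoints (MI, stroke, and death", at a two-sided alpha below 0.01, "assuming 8% of subjects experience the endpoint". The next sentence says that 800 subjects allow an HR of 1.9 with p=0.04 ("lower bound of the 95% CI of 1.2) can be detected"). The paragraph also says follow-up continues until at least 80 ischemic events. It gives no formula and no high/low split.

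Three other places bear on these figures:

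- Protocol 4.1 plans about 12 months of enrolment and at least 18 months of follow-up for the last subject, and adds: "Based on an annual ischemic event rate of 10%, the overall length of participation in the study is anticipated to be up to 3 years".
- SAP 5.7.1 sets the decision rule: FcγRIIa will be "declared to be associated with cardiovascular risk if the 2-sided p-value from this model is < 0.05".
- Protocol 2.3 says of the pilot: "MI, stroke, and death were uncommon (8% of all patients) in patients who had had an MI".

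**The concern.** Eight percent of 800 is 64 events. That is few for 95% power at alpha 0.01 against a hazard ratio of 2, and it is below the 80-event minimum in the same paragraph. In the companion sentence, an HR and its lower limit fix the standard error and so fix the p-value. A lower limit as far from 1 as 1.2 does not fit a p-value as close to 0.05 as 0.04.

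This paragraph is the only power justification for the primary endpoint in either document. If the study closed near its minimum of 80 events with a null or borderline result, a reader would take a 2-fold effect to have been excluded with 95% power at alpha 0.01, when the figure is about 70%. The p-value and limit pair also leaves it unclear what effect the study is meant to detect.

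**Working it through.** **Inputs.** N=800, 8% with the endpoint, "a 2-fold greater incidence of cardiovascular endpoints" (taken as HR 2), two-sided alpha 0.01 (the most favourable value, since the text says below 0.01), and at least 80 events: all from SAP 5.10 and Protocol 9.2. The high/low split is not given. I assume 50:50, with 55:45 as the alternative because Protocol 2.3 reports 55% high among the pilot's higher-risk subjects.

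**Reading of the 8%.** I take it as the proportion of all subjects. That matches the pilot's 8% of all patients, and the bleeding sentence in the same section names the low group when it means that group: "5% of subjects experience bleeding in the low FcγRIIa expression group".

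**Attempt to reproduce the 95%.** Schoenfeld: power = Φ(ln 2 × √(d·q·(1−q)) − z), where d is events, q the proportion high, and z = 2.576 at alpha 0.01.

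- d = 64, q = 0.50: 0.693 × √16 − 2.576 = 0.197, power 57.8%.
- d = 64, q = 0.55: 0.693 × √15.84 − 2.576 = 0.183, power 57.3%.

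Other methods on the same inputs agree broadly. A two-proportion test (5.33% vs 10.67% at 50:50) gives 58%, or 54% at 55:45. Freedman's formula gives 54%, and a log-rank simulation 52–55%. Converting the cumulative risks to an HR of about 2.06 gives 62%. None approaches 95%.

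**Other readings, HR 2:**

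| Reading | Events | Power, alpha 0.01 | Power, alpha 0.05 |
|---|---|---|---|
| 8% of all subjects | 64 | 57–58% | 79% |
| 80-event minimum | 80 | 69–70% | 87% |
| 8% low group, 16% high group | 96–99 | 79–82% | 92–94% |
| 10% per year, planned timeline | about 145 | 94% | 99% |

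In the third row, converting the risks to HR 2.09 gives 85–86% at 0.01 and about 95% at 0.05.

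The last row assumes a constant hazard of 0.10 per year, uniform 12-month enrolment, cutoff 18 months after the last enrolment, and no dropout. The event probability is 1 − (e^−0.15 − e^−0.25)/0.10 = 0.181, and 800 × 0.181 ≈ 145. Reading 10% as an annual risk (hazard 0.105) gives about 152 events and 95% at alpha 0.01.

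**Events needed for 95% at alpha 0.01.** (2.576 + 1.645)² / (q(1−q)(ln 2)²) gives 149 at 50:50 and 150 at 55:45, about 19% of 800 rather than 8%.

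**Companion sentence.**

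- From HR 1.9 and limit 1.2: SE = (ln 1.9 − ln 1.2)/1.96 = 0.234; z = 0.642/0.234 = 2.74; p = 0.006. Over all rounding (HR 1.85–1.95, limit 1.15–1.25), p runs from 0.002 to 0.013 and never reaches 0.04.
- From HR 1.9 and p = 0.04: z = 2.054; SE = 0.642/2.054 = 0.313; lower limit = exp(0.642 − 1.96 × 0.313) = 1.03. This corresponds to about 41 events.
- From 80 events at 55:45: SE = 1/√(80 × 0.2475) = 0.225; lower limit 1.22; p = 0.004.

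The HR and the limit therefore fit 80 events. The printed 0.04 may be a slip for 0.004, but that is inference.

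**The case against.** The strongest reply is that 57% describes a study that will not be run. Follow-up cannot end by plan at 64 events: it needs at least 80 events and 18 months for the last subject, and the test is at 0.05. At the Protocol's own annual rate the stated 95% nearly reproduces, so the faulty number may be the 8% rather than the power. This stands as a caution: 57% is the power under the stated assumptions, not a forecast. It does not rescue the text, because about 145 events is 18% of subjects and the plan guarantees only 80.

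Several smaller points also stand:

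- The 10% rate is not in the sample size section, so the only clash inside that section is 64 events against at least 80. Since 80 is a minimum, 145 expected events do not contradict it.
- Claiming power at a stricter alpha than the decision rule is conservative, not an error in itself.
- The section presents the study mainly as sized for a prediction model by events per predictor, with power in support.
- The exact figure varies with the method, from about 52% to 62%.

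None of these makes the power claim follow from its inputs or reconciles p=0.04 with a limit of 1.2.

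**Conclusion.** The paragraph is wrong as written in both documents. At the stated two-sided 0.01, its inputs give about 57–58% power (Schoenfeld) against a claimed 95% or more. The most favourable reading of the 8% stays at or below about 86%. Figures near 95% appear only when an input is changed, such as the alpha or the event rate. The p-value and lower limit are incompatible for any event count or split.

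The power figures rest on proportional hazards and 50–55% of subjects high. The second result needs only the usual normal approximation for the log hazard ratio. Two further assumptions flatter the study: no loss to follow-up, and no subjects excluded for missing baseline FcγRIIa, although SAP 5.9 excludes them. All the figures concern a high/low contrast, whereas the primary test in SAP 5.7.1 uses continuous FcγRIIa adjusted for eleven covariates. The stated power does not describe that test directly.

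**What to change.** Replace the two sentences in SAP 5.10 and Protocol 9.2 with one consistent statement at the analysis alpha of 0.05, naming the formula and the split. For example:

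> With 80 subjects having a first event and 55% in the high group, power for HR 2.0 is 87% at two-sided alpha 0.05 (69% at 0.01), and an observed HR of 1.9 would have p=0.004 and a lower 95% limit of 1.2 (Schoenfeld). With the roughly 145 first events expected at 10% per year and 18 months' minimum follow-up, power for HR 2.0 is 99% (94% at alpha 0.01).

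Delete the 8% assumption, or reconcile it with the 80-event minimum and the 10% annual rate. State whether the 80 events are subjects with a first event, since later events are also recorded and the power depends on first events. Say that the calculation is for a high/low contrast, or add one for continuous FcγRIIa.

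Recalculate the bleeding sentence in the same edit. Its 95% for HR 1.93 does not reproduce either: about 58 events give roughly 68–71% at 50:50, and 95% needs 121.

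The cost is one paragraph in each document, with no extra subjects and no design change. The power guaranteed at the 80-event minimum will read less favourably than the present 95%.
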